7.2.5.1. Statistical Methodology Specification

Key Secondary Statistical Analyses
Endpoint
Proportion of participants with plasma HIV-1 RNA <50 c/mL at Week 48 using the FDA Snapshot algorithm (Intent-to-Treat Exposed [ITT-E] population)
Snapshot Dataset

 As described in Section 7.1.5.1 and Section 13.11
Model Specification

 As specified in Section 7.1.5.1 but with HIV-1 RNA <50 c/mL (Snapshot Success) replacing Plasma HIV-1 \geq 50 c/mL (Snapshot 'HIV-1 RNA\geq50')
Model Results Presentation

 Adjusted CMH estimate of the difference in the proportion of participants with plasma HIV-1 RNA <50 c/mL at Week 48 between each treatment group (Q4W – Current ART) and corresponding 95% confidence interval. Non-inferiority will be concluded if the lower bound of the two-sided 95% confidence interval for the CMH adjusted treatment difference (Q4W – Current ART) is greater than -10%.
Subgroup Analyses

 Treatment Heterogeneity across randomization strata: 
 As specified in Section 7.1.5.1 but with Snapshot Success (HIV-1 RNA <50 c/mL) replacing Snapshot HIV-1 RNA \geq 50 c/mL.
Sensitivity and Supportive Analyses

 Per-protocol population analysis: To assess the impact of important protocol deviations, statistical analysis will be repeated using the Per-protocol population and compared for consistency with the results from the primary ITT-E population analysis.

8. SAFETY ANALYSES

The safety analyses will be based on the Safety population, unless otherwise specified.

For the week 48 primary analysis and IDMC, outputs will be presented for the Maintenance Phase unless otherwise specified.

For the Week 48 primary analysis, a set of separate outputs will also be presented for the oral lead-in period at Maintenance phase, including summary of adverse events, SAE, AE leading to withdrawal, post-baseline emergent chemistry/haematology abnormality, subjects with hepatobiliary abnormality criteria et al.

For the Week 96 secondary analysis, outputs will be presented for the Maintenance + Extension phases for subjects randomized to receive CAB +RPV LA, and will be presented for the Extension phase only for Extension Switch Population (ESP). Adverse events by System Organ Class and Maximum Toxicity for Long-term Follow-up Phase will also be summarized.

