
window collection; clarify text for patient reported outcome endpoints and timings for completion of questionnaires relative to other clinical assessments and procedures, add clarification for prohibited medication information; remove information in the Appendix requiring collection of pregnancy information for female partners of male study participants; incorporate updates from country-specific amendments No 1, and No 2. into a global protocol amendment; add text that additional details of the injection device used by sites for IM administration including, but not limited to functional performance, may also be collected within the eCRF; clarify that commercial availability of CAB LA + RPV LA includes availability through local public/government health sectors; add allowance that in exceptional circumstances, local labs can be reviewed and approved by the Medical Monitor for consideration of participant eligibility; add information that Screening HLA-B*5701 result is not required to inform eligibility status; add other minor corrections and edits to protocol text.
		
2015N252007_04	2017-NOV-02	Amendment No. 4

The reason for amendment 4 is to acknowledge the potential rollover of eligible 201585 (ATLAS) study participants following the Week 52 visit and completion of time point for the primary analysis to the 207966 (ATLAS-2M) study examining the efficacy, safety and tolerability of CAB LA + RPV LA administered every 4 weeks (Q4W) compared to CAB LA + RPV LA administered every 8 weeks (Q8W). Specifications for the procedural rollover of 201585 participants are included within amendment #4. Due to the planned transition of eligible participants to ATLAS-2M following the time point completing Week 48 primary analysis, the snapshot virologic response at Week 96 and in the Extension Phase for ATLAS is no longer valid and has been replaced with the proportion of participants with plasma HIV-1 RNA < 50 c/mL over time including Week 96. Exploratory analyses evaluating the effect of patient characteristics on virologic and immunologic responses in the treatment arms are also limited to a Week 48 analysis. The reporting timeline of pregnancy event and follow-up pregnancy form has been updated from 2 weeks to 24 hrs of identification of a pregnancy event, and within 24 hrs of investigator awareness of pregnancy outcome, respectively. Updated references for the cabotegravir and rilpivirine investigator brochures have been added.
		

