
transition to CAB LA + RPV LA in the Extension Phase
	
through Week 96
 
 • Absolute values and change from Baseline in plasma HIV-1 RNA over time including Week 96 • Absolute values and changes from Baseline in CD4+ cell counts over time including Week 96 • Incidence of disease progression (HIV-associated conditions, acquired immunodeficiency syndrome [AIDS] and death) • Incidence and severity of AEs and laboratory abnormalities over time including Week 96 • Proportion of participants who discontinue treatment due to AEs over time including Week 96 • Absolute values and changes in laboratory parameters over time including Week 96 • Incidence of treatment emergent genotypic and phenotypic resistance to CAB, RPV, and other on study ART through Week 96

To assess the acceptance of pain and injection site reactions following injections
	
 • Change from Week 5 in Dimension scores (“Bother of ISRs”, “Leg movement”, “Sleep”, and “Injection Acceptance”) and individual item scores assessing pain during injection, anxiety before and after injection, willingness to be injected in the future and overall satisfaction with mode of administration over time using the Perception of iNjection questionnaire (PIN) • Proportion of participants considering pain and local reactions following injection to be extremely or very acceptable based on the acceptability score over time using the Perception of iNjection questionnaire (PIN)

To assess degree of health-related quality of life (HRQoL)
	
 • Change from Baseline in HR QoL using the HIV/AIDS-targeted quality of life questionnaire (HAT QoL) short form at Week 24, Week 48, Week 96 (or Withdrawal).

To assess the health status
	
 • Change from Baseline in health status at Week 24, Week 48, and Week 96 (or Withdrawal) using the 12-item Short Form Survey (SF-12).

To assess treatment satisfaction of CAB LA + RPV LA compared to
	
 • Change from baseline in total “treatment satisfaction” score, and individual items scores of the HIVTSQs at

Objectives	Endpoints
continuation of current ART	Weeks 4b, 24, 44, 96 (or Withdrawal) 
 Change in treatment satisfaction over time using the HIVTSQc at Week 48 (or Withdrawal)

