- This calculation will not be performed for subjects who have indicated current or past myocardial infarction conditions on the eCRF. These subjects will not be included in summary statistics of risk, but will be counted in the highest category of risk in the summary by category.

Extent of Exposure

- Exposure to CAB+RPV (oral lead-in) and CAB LA+RPV LA will be calculated from the IP eCRF pages. Exposure to Current ART will be calculated from the CONART eCRF pages.

Q4W IM arm:

- For Maintenance Phase:
 - Exposure to CAB + RPV (oral lead-in) = IP (oral lead-in) stop date- IP (oral lead-in) start date +1
 - Exposure to CAB LA + RPV LA = Number of IP injections received during Maintenance Phase
 - Overall exposure to IP = min [Date of nominal Week 52 visit, max(Date of last IP injection +35, date of last oral CAB/RPV)] - Oral lead-in CAB/RPV Start Date +1
- For Maintenance + Extension Phase
 - Exposure to CAB LA + RPV LA = Number of IP injections received during Maintenance Phase + Extension Phase
 - Overall Exposure to IP = (Date of last IP injection +35, - Oral CAB/RPV Start Date +1

Current ART arm

- For Maintenance Phase:
 - If a subject continues to Extension phase
Exposure = (IP Start Date at extension phase – 1) – Day 1 DOV + 1
 - If a subject discontinues prior to Nominal Week 52,
Exposure = Min (Current ART stop date, withdrawal date) – Day 1 DOV + 1
 - If a subject chooses to complete the study participation at Nominal Week 52 and not to continue to Extension phase, then
Exposure=completion date – Day 1 DOV +1

Current ART stop date is the last permanently stop date among all ARTs taken during Maintenance phase.

- For Extension Phase (Extension Switch Population only):
 - Exposure to CAB + RPV (oral lead-in) = IP (oral lead-in) stop date- IP (oral lead-in) start date +1
 - Exposure to CAB LA+ RPV LA = Number of IP injections received during Extension Phase
 - Overall exposure to IP = max(Date of last IP injection+35, date of last oral CAP/RPV) - Oral CAB/RPV lead-in Start Date +1
- Duration of dosing in subject years will be calculated as the sum of subject duration of dosing in days (across all subjects)/365.25
- Subjects who were randomised to CAB LA+RPV LA but did not report a IP start date will be categorised as having zero days of exposure.
- Subjects who were randomised to Current ART but withdrew on Day1 will be categorised as having zero days of exposure.

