13.7. Appendix 7: Reporting Standards for Missing Data

13.7.1. Premature Withdrawals

Element	Reporting Detail
General	
 ● Subject study completion (i.e. as specified in the protocol) was defined as: 
 ○ Randomly assigned to either treatment group, completed the randomized Maintenance Phase including the Nominal Week 52 visit, and did not enter the Extension Phase; ○ Randomly assigned to either treatment group, completed the randomized Maintenance Phase including the Nominal Week 52 visit, and entered and completed the Extension Phase (defined as remaining on study until transitioning to ATLAS-2M, or commercial supplies of CAB LA + RPV LA become locally available, or development of CAB LA + RPV LA is terminated). 
Participants who withdraw from CAB LA + RPV LA and go into the Long-Term Follow Up Phase will be considered to have prematurely withdrawn from the study, even if they complete the 52-week follow-up phase. In addition to the 52 week Long-Term Follow-Up Phase required for participants randomized to CAB LA + RPV LA, an in-clinic Follow-Up visit will be conducted approximately 4 weeks after the last dose of study medication for participants randomized to the Current ART arm with ongoing AEs, SAEs, and also any laboratory abnormalities that are considered to be AEs or potentially harmful to the participant, at the last on-study visit. Assessments at the Follow-up visit should reflect any ongoing complaints (e.g., blood draws to follow a laboratory abnormality). Follow-Up visits are not required for successful completion of the study.
 
 ● Withdrawn subjects were not replaced in the study. ● All available data from participants who were withdrawn from the study will be listed and all available planned data will be included in summary tables and figures, unless otherwise specified. ● Withdrawal visits will be slotted as per Appendix 3: Assessment Windows or will be summarised as withdrawal visits.

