13.11. Appendix 11: Snapshot Algorithm Details

Detailed Algorithm Steps

- Consider an analysis visit window for Week X (e.g. Week4, ...Week 24, Week 48 et al). The Window for Week 24/48 visit is defined in Table 11 (e.g. window for Week 48 is ± 6 Week: $295 \leq \text{Study Day} \leq 378$) and in Table 9 for other visits through to Nominal Week 52 at Maintenance Phase. The Snapshot Analysis at post Maintenance Phase will not be appropriate because a large portion of responders will be switched to other studies and not all subjects would have the chance to reach same timepoint.
- The HIV1-RNA threshold of 50, 200 copies/mL will be analysed, respectively, in this study
- The analysis window 'Week 48' and HIV1-RNA threshold of '50 copies/mL' are used for the purpose of illustration. A subject's Snapshot response and reason at Week 48 are categorized as below.
 - HIV1-RNA < 50 copies/mL
 - HIV1-RNA ≥ 50 copies/mL
 - Data in window not below 50
 - Discontinued for lack of efficacy
 - Discontinued for other reason while not below 50
 - Change in background therapy*
 - No Virologic Data at Week 48 Window
 - Discontinued study due to AE or death
 - Discontinued study for other reasons
 - On study but missing data in window

* Note: since changes in ART are not permitted in this protocol, all such subjects who change ART during the maintenance phase will be considered 'HIV1-RNA ≥ 50 copies/mL'. if the change in ART is made prior to an analysis timepoint. Subjects with protocol permitted oral bridging treatment will not be considered ' HIV1-RNA ≥ 50 copies/mL' due to 'change in ART'.

- The steps in determining response and reasons are indicated in Table below, in the order stated.

Detailed steps		
Please note that the following scenarios will NOT be penalized Per Snapshot algorithm (i.e. please excluding these scenarios from Condition 1-4).		

 • Dose reduction, dropping a component, or change in formulation (e.g. 'Tivicay + Kivexa' to 'Triumeq' with the identical ingredients) 		
Condition ('Week 48' indicates Week 48 window)	Response	Reasons
1. If non-permitted change in background therapy prior to Week 48	HIV1-RNA ≥ 50	Change in background therapy
2.If permitted change ^[a] in background therapy prior to Week 48 AND the latest on-treatment VL prior to/on the date of change is ≥ 50 c/m (NA to this study)	HIV1-RNA ≥ 50	Change in background therapy

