13.13.7. Safety Tables

Safety Tables (Displays will be for both treatment arms, unless specified)					
No.	Population	IDSL / TST ID / Example Shell	Title	Programming Notes	Deliverable [Priority]
Exposure					
3.1.	Safety	Shell TS1.1	Summary of Extent of Exposure to Investigational Product – Maintenance Phase	CS Core	WK48, 96, EOS
3.2.	Safety	Shell TS1.1	Summary of Extent of Exposure to Investigational Product – Maintenance Phase + Extension Phase (for Q4W IM arm)	CS Core (only for Q4W arm)	WK48, 96, EOS
3.3.	ESP	Shell TS1.1	Summary of Extent of Exposure to Investigational Product – Extension Phase only	CS Core (only for Current ART)	WK48, 96, EOS
3.4.	Safety	Shell TS1.2	Summary of Needle Length and Gauge for CAB Injection - Maintenance Phase	(only for Q4W arm)	WK48
3.5.	Safety	Shell TS1.2	Summary of Needle Length and Gauge for RPV Injection - Maintenance Phase	(only for Q4W arm)	WK48
3.6.	Safety	Shell TS1.3	Summary of Adherence to Q4W IM Dosing Schedule (Maintenance phase)	(only for Q4W arm) please refer to Section 13.6.2 -- Adherence to CAB/RPV Injection Schedule	WK48
Adverse Events					
3.7.	Safety	AE1	Summary of All Adverse Events by System Organ Class – Maintenance Phase	CS Core (optional)	WK48
3.8.	Safety	AE5B	Summary of All Adverse Events by System Organ Class and Maximum Toxicity – Maintenance Phase	CS Core	HL, WK48
3.9.	Safety	AE5B	Summary of All Adverse Events by System Organ Class and Maximum Toxicity – Maintenance + Extension Phase	CS Core ((only for Q4W arm)	WK48, 96, EOS
3.10.	ESP	AE5B	Summary of All Adverse Events by System Organ Class and Maximum Toxicity – Extension Phase	CS Core (only for Current ART)	WK48, 96, EOS

Safety Tables (Displays will be for both treatment arms, unless specified)					
No.	Population	IDSL / TST ID / Example Shell	Title	Programming Notes	Deliverable [Priority]
3.11.	Safety	AE5B	Summary of All On-treatment Adverse Events by System Organ Class and Maximum Toxicity – Maintenance Phase	CS Core	WK48
3.12.	LTFU	AE5B	Summary of All Adverse Events by System Organ Class and Maximum Toxicity – Long-term Follow-up Phase	CS Core	WK 96, EOS
3.13.	Safety	AE5B	Summary of All Adverse Events by System Organ Class and Maximum Toxicity – Oral Lead-in Period at Maintenance phase	CS Core (for Q4W arm only)	HL, WK48
3.14.	Safety	AE3	Summary of Common Adverse Events (>=5%) by Overall Frequency – Maintenance Phase	CS Core	WK48

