3.31.	Safety	AE1	Summary of Adverse Events Leading to Withdrawal/Permanent Discontinuation of Investigational Product by System Organ Class– Maintenance Phase	CS Core	HL, WK48
3.32.	Safety	AE1	Summary of Adverse Events Leading to Withdrawal/Permanent Discontinuation of Investigational Product by SOC – Maintenance + Extension Phase	CS Core(for Q4W arm only)	WK48, 96, EOS
3.33.	ESP	AE1	Summary of Adverse Events Leading to Withdrawal/Permanent Discontinuation of Investigational Product by SOC – Extension Phase	CS Core(for Current ART arm only)	WK48, 96, EOS

Safety Tables (Displays will be for both treatment arms, unless specified)					
No.	Population	IDSL / TST ID / Example Shell	Title	Programming Notes	Deliverable [Priority]
3.34.	Safety	AE1	Summary of Adverse Events Leading to Withdrawal/Permanent Discontinuation of Investigational Product by SOC – Oral Lead-in Period at Maintenance Phase	CS Core(for Q4W arm only)	WK48
3.35.	Safety	AE1	Summary of Common (>=5%) Non-Serious Adverse Events – Maintenance Phase	CS Core	WK48
3.36.	Safety	EudraCT Non-serious AE AE15	Summary of Subjects and Number of Occurrences of Common (>=5%) Non-Serious Adverse Events by System Organ Class – Maintenance Phase	CS Core for FDAAA and EMA disclosure requirements. EudraCT Use macro TD_AE4VCTR for New Data Disclosure HARP Reporting Tools	WK48
3.37.	Safety	EudraCT SAE AE16	Summary of Subjects and Number of occurrences of SAEs, Drug-related AEs, Fatal SAEs, and Drug-related SAEs – Maintenance Phase	CS Core for FDAAA and EMA disclosure requirements. EudraCT	WK48
3.38.	Safety	Shell TS2.1	Summary of Cumulative Adverse Events by Visit– Maintenance Phase	Please note that this table only display AEs occurring >=5% subjects during Maintenance phase	WK48
3.39.	Safety	Shell TS15	Summary of Adverse Events by System Organ Class and Baseline ART Third Agent Class – Maintenance Phase		WK48
Injection Site Reaction Adverse Events					
3.40.	Safety	Shell TS2.2	Summary of Injection Site Reaction Adverse Events (Event-Level Summary) –Maintenance Phase	(for Q4W arm only)	HL, WK48
3.41.	Safety	Shell TS2.2	Summary of Injection Site Reaction Adverse Events (Event-Level Summary) –Maintenance + Extension Phase	(for Q4W arm only)	WK96, EOS
3.42.	ESP	Shell TS2.2	Summary of Injection Site Reaction Adverse Events (Event-Level Summary) –Extension Phase	(for Current ART arm only)	WK96, EOS

Safety Tables (Displays will be for both treatment arms, unless specified)					

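### Week 96 and end-of-study AE percentages for the Q4W arm make no allowance for participants who leave for ATLAS-2M after Week 52, so they understate the 96-week incidence of events that continue after that point

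*SAP*

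**What the plan says.** - **Reporting period.** SAP Section 8 states that at Week 96 safety "outputs will be presented for the Maintenance + Extension phases for subjects randomized to receive CAB +RPV LA". The Extension Switch Population (ESP) is reported over the Extension only.
- **Endpoint.** Section 2.2 lists, among the Extension Phase secondary endpoints, AE incidence and severity and "Proportion of participants who discontinue treatment due to AEs over time including Week 96".
- **Displays.** Section 13.13.7 lists Table 3.9, "Summary of All Adverse Events by System Organ Class and Maximum Toxicity – Maintenance + Extension Phase", and Table 3.32, "Summary of Adverse Events Leading to Withdrawal/Permanent Discontinuation of Investigational Product by SOC – Maintenance + Extension Phase". Tables 3.18, 3.22 and 3.27 cover drug-related AEs, SAEs and drug-related SAEs over the same period. All are AE1 or AE5B displays for the Q4W arm, due at Week 48, Week 96 and end of study. No rate, Kaplan-Meier or cumulative-incidence version is listed. The cumulative AE-by-visit table (3.38) covers the Maintenance Phase only.
- **Follow-up.** The Introduction gives the reason for protocol amendment 4: "Due to the planned transition of eligible participants to ATLAS-2M following the time point completing Week 48 primary analysis", the Snapshot response at Week 96 was no longer valid. Appendix 11 adds that "a large portion of responders will be switched to other studies and not all subjects would have the chance to reach same timepoint". Section 13.7.1 counts "remaining on study until transitioning to ATLAS-2M" as one way of completing the Extension.
- **Exposure.** Section 13.6.2 says: "Duration of dosing in subject years will be calculated as the sum of subject duration of dosing in days". No AE display is said to use this total as a denominator.

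**The concern.** The plan recognises that follow-up after Week 52 is unequal by design. It changes efficacy accordingly: the Week 96 virologic endpoint becomes an observed-case proportion. The AE endpoints over the same calendar time keep the full arm as denominator.

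A participant who transfers at Week 52 without an event stays in that denominator and counts as event-free, although Weeks 52 to 96 (44 weeks) were not observed under this protocol. Because transfer counts as completion, it will not appear in the disposition tables as early withdrawal. The percentage then mixes people followed for about one year with people followed for nearly two or more, and it is lower than the risk of an event by Week 96 whenever events continue after Week 52. Late-onset events, which are a main reason for longer follow-up, are affected most.

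**Working it through.** The SAP gives no incidence figure, leaving fraction or event timing, so there is no stated value to reproduce. All inputs below except the time points are assumptions.

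**Inputs**
- Departure at Week 52 and target time at Week 96 (SAP Introduction, Sections 2.2 and 2.3).
- f = fraction of the Q4W arm leaving at Week 52: assumed 30%, 50%, 70%, 90%.
- p = risk of a first event per 48 weeks: assumed 10%, then 5% and 20%.
- Constant hazard, and everyone who does not leave is followed to Week 96.

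**Formulas**
- Incidence by Week 52: C52 = 1 − (1 − p)^(52/48)
- Incidence by Week 96: C96 = 1 − (1 − p)^2
- Expected crude percentage: f × C52 + (1 − f) × C96

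**With p = 10%:** C52 = 1 − 0.9^1.0833 = 10.79% and C96 = 1 − 0.81 = 19.0%.

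| f leaving | Mean potential follow-up, 52f + 96(1 − f) | Crude % | Shortfall relative to 19.0% |
|---|---|---|---|
| 30% | 82.8 weeks | 0.3 × 10.79 + 0.7 × 19.0 = 16.5 | 13% |
| 50% | 74.0 weeks | 0.5 × 10.79 + 0.5 × 19.0 = 14.9 | 22% |
| 70% | 65.2 weeks | 0.7 × 10.79 + 0.3 × 19.0 = 13.3 | 30% |
| 90% | 56.4 weeks | 0.9 × 10.79 + 0.1 × 19.0 = 11.6 | 39% |

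**Other risks.** At p = 5%, C52 = 5.41% and C96 = 9.75%; the shortfall runs from 13% (f = 30%) to 40% (f = 90%). At p = 20%, C52 = 21.47% and C96 = 36.0%; it runs from 12% to 36%. Over p = 5-20% the range is therefore 12-40%.

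**Event timing.** Let s be the share of the 96-week events that occur by Week 52. Then crude / true = f × s + (1 − f), so the relative shortfall is f × (1 − s). The constant-hazard case at p = 10% has s = 10.79 / 19.0 = 0.57. If s = 0.90, the shortfall is 0.25 × 0.10 = 2.5% at f = 25% and 0.90 × 0.10 = 9% at f = 90%. If s = 1, it is zero.

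**Effect of the remedy.** Under constant hazard h, the expected time at risk to first event is [f × C52 + (1 − f) × C96] / h. Events divided by time at risk therefore give h for every f, and 1 − exp(−96h) returns 19.0%. A Kaplan-Meier estimate censored at transition does not need the constant-hazard assumption; it needs transition to be unrelated to the risk of the event.

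**The case against.** The strongest reply is that nothing inferential depends on these tables. Section 3 plans no comparison between arms at Week 96, and the randomized safety comparison uses the Maintenance Phase tables. The endpoint is worded as a proportion, and the tables are titled by phase, not as 96-week risk. Unequal follow-up will also be visible in the same deliveries, through exposure Tables 3.2 and 3.3 and accountability Tables 1.11 and 1.12. All of this stands, and it limits the weight of the point. It does not remove it: the endpoint is stated over time including Week 96, and a reader cannot work out the 96-week incidence from a separate exposure table.

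A reader might infer more than the documents support:
- **That all ten Week 96 AE tables suffer from Week 52 departures.** The ESP tables (3.10, 3.19, 3.23, 3.28, 3.33) include only Current ART participants dosed in the Extension (Section 4). Nobody who left at Week 52 is in that denominator. Their only problem is variable follow-up within the Extension.
- **That follow-up is ignored everywhere.** Injection site reactions are partly covered: Section 8.4, Table 5, note 21 includes a rate per injection visit, and Tables 3.44 and 3.45 are due at Week 96 and end of study.
- **That the display format is certain.** The mock shells are a separate document. The n (%) reading rests on the endpoint wording, the display types and the categorical-data standard in Section 13.5.2.
- **That the subject-years in Section 13.6.2 are ready to use.** They are total dosing time, not time at risk to first event.

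**Conclusion.** The point holds for the Q4W Maintenance + Extension tables. The plan reports whole-arm percentages over a period in which, by its own account, a large portion of responders cannot reach the later time points, and it lists no measure that allows for this. The direction is certain for events that continue after Week 52.

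The size is not known. It is 13-39% at a 10% risk per 48 weeks with 30-90% leaving, and 12-40% over risks of 5-20%, all under constant hazard. It is only about 2.5-9% if 90% of the 96-week events occur by Week 52 (25-90% leaving), and zero if all do. A shortfall near 40% should not be taken as a property of this trial, because the SAP gives neither the leaving fraction nor the event timing.

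The Week 48 randomized comparison is not affected. This is a cheap improvement to a descriptive secondary analysis, not an error that threatens the trial's conclusions.

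**What to change.** For the Week 96 and end-of-study deliveries, amend Section 8 and the display list in Section 13.13.7:

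1. Report AE discontinuation through Week 96 for the Q4W arm as a Kaplan-Meier or cumulative-incidence estimate, censored at ATLAS-2M transition or last contact. The SAP already specifies Kaplan-Meier methods with censoring rules for treatment-related discontinuation, to Week 48 only (Section 13.6.4, Appendix 15, Table 2.14).
2. Add first-event rates per 100 participant-years at risk to the overall AE, SAE, drug-related AE and AE-withdrawal rows, for the Q4W arm and the ESP.
3. Label the n (%) in these tables as not adjusted for follow-up.

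**Cost.** A new time-to-first-event derivation and slightly longer tables, with no new data collection. Restricting the rates to the overall rows avoids a derivation for every term and grade. A pooled rate assumes a roughly constant hazard and can mislead for early-onset events, so it should stand beside the n (%), not replace it.
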